Study Protocol

Official Title of the Study:

Forgetting Alcohol: A Double-blind, Randomized Controlled Trial Investigating Memory Inhibition Training in Young Binge Drinkers

NCT ID: not yet assigned

Date: February 5, 2019

Study Design and Setting

The present study will be composed of three different phases: 1) behavioral and electrophysiological analyses of MI abilities in young BDs as compared to age-matched non/low-drinkers; 2) a double-blind, randomized controlled trial (RCT) aiming at assessing the effects of a MI training protocol at the behavioral and electrophysiological level; and 3) monitoring of self-reported alcohol consumption and alcohol craving 10 days and 3 months after the MI training.

Target population

The volunteers will be ninety college students (~50% female), aged between 18 and 23 years: 45 non/low-drinkers and 45 BDs matched for age and gender. All participants will be recruited through a screening questionnaire administered in the classroom of several courses taught at the University of Minho (UM). The screening will include the Alcohol Use Disorder Identification Test (AUDIT) [1] along with other questions concerning alcohol and drugs use.

Inclusion and exclusion criteria

To participate in the study, college students must meet the following eligibility criteria: report (i) drinking 5 or more drinks on one occasion at least once a month, and (ii) drinking at a speed of at least two drinks per hour during these episodes (which brings blood alcohol concentration to 0.08 gram percent or above [2], in order to be classified as BDs; or report (i) never drinking 5 or more drinks on each occasion and (ii) having an AUDIT score ≤ 4 , to be considered as non/low-drinkers. The students who fulfilled the inclusion criteria will perform a clinical interview that will assess the following exclusion

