criteria: a) use of illegal drugs except cannabis (as determined by the Drug Use Disorders Identification Test-Extended [DUDIT-E], [3]); b) alcohol abuse (i.e., AUDIT \geq 20); consumption of medical drugs with psychoactive effects (e.g., sedatives or anxiolytics) during the two weeks before the experiment; c) personal history of psychopathological disorders (according to DSM-V criteria); d) history of traumatic brain injury or neurological disorder; e) family history of alcoholism or diagnosis of other substance abuse; f) occurrence of one or more episodes of loss of consciousness for more than 20 minutes; g) non-corrected sensory deficits; h) Global Severity Index (GSI) $>$ 90 (Symptom Checklist-90-Revised questionnaire [SCL-90-R], [4]) or a score above 90 in at least two of the symptomatic dimensions.

Quality assurance and randomization

The protocol will be implemented by three skilled researchers with expertise in behavioral and EEG assessments and tDCS interventions. Researchers will not be aware of the results of the pre-training EEG assessment and will be blind to the randomization procedure that will follow. The randomization of the BD groups will be performed by an independent researcher using Microsoft Excel. BDs will receive one of the following interventions: 1) Combined training (verum CT and tDCS applied over the right dorsolateral prefrontal cortex); 2) Cognitive training (active CT and sham tDCS); or 3) Control (sham CT and sham tDCS). Based on this experimental procedure, it is expected that researchers will be able to answer the following research questions:

1. How does BD affect alcohol-related MI in young adults? Namely, are the behavioral and electrophysiological MI mechanisms - specifically those related to the suppression of alcohol-related memories - altered in BDs when compared to non/low-drinkers?

2. What is the effect of a MI training on behavioral TNTA task performance?

Specifically, will the BDs show a reduced recollection of no-think images - mainly for alcoholic no-think images – after training?

3. Are the electrophysiological correlates underlying MI mechanisms and alcohol cue reactivity changed by MI training?

4. Will the MI training reduce alcohol consumption and craving levels at 10-day and 3-month follow-ups?

Experimental tasks

Alcohol Cue Reactivity (ACR) task

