EEG data will be recorded using the ActiveTwo Biosemi System (Biosemi, Inc.) from 64 electrodes placed according the 10-10 system [12] and digitized at a 512 Hz rate. Vertical and horizontal electrooculogram activity will be recorded to control for eye movements and blinks. Two additional electrodes will be placed on the mastoids, bilaterally, to provide the signal offline reference. Electrode impedances will be kept below 20 kΩ and the EEG signal will be filtered on-line with a 0.01–100 Hz band pass filter.

T3: MI Training Sessions

After the pre-training EEG assessment (T2), BDs will be randomly assigned to one of the three training subgroups: *a) Combined training; b) Cognitive training; or c) Control*. The participants' allocation to the training group will be done by an independent researcher who will be responsible to program the tDCS parameters. Thus, both participants and research team will be blind to the randomization procedure.

During T3, subjects will perform the variation of the TNTA task corresponding to the group to which they will be assigned. After the first phase of the task (i.e., Learning Phase), neuromodulation (sham or active) will be performed using tDCS - a non-invasive, painless and safe brain stimulation method capable of modulating cortical excitability through a weak constant electric current induced from two surface electrodes placed on the scalp [13]. Twenty minutes of 2 mA direct current will be applied to the scalp using a saline-soaked pair of 35 cm² surface sponge electrodes, through an Eldith DC Stimulator Plus (Neuroconn, Germany). To stimulate the right DLPFC, the anodal electrode will be placed over F4 according to the 10-20 international system for EEG electrode placement.

The cathode electrode will be placed over the contralateral supraorbital area. During the active simulation, the current will fade in for 15 seconds, will be constant at 2 mA for 20 minutes, and then will fade out for 15 seconds. During the sham stimulation, the electric current will fade in during 15 seconds until reaching 2 mA, then will be constant at 2 mA for 15 seconds and will fade out for 15 seconds. This procedure makes both active and sham stimulation indistinguishable for the participants. Before and after the training sessions, participants will answer to a continuous Visual Analog Scale that allows checking for possible secondary effects of the electrical stimulation.

T4: Post-training EEG Assessment

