At T4, participants will perform the ACR and TNTA tasks under the same procedure to the one undertaken during the T2.

T5: Monitoring of alcohol consumption and alcohol craving.

Ten days after the post-training EEG assessment, the primary craving and alcohol consumption outcomes will be assessed. For this purpose, we will administer the PACS, the ACQ-SF-R and the AUDIT. Additionally, three months post-intervention, BDs will answer the same questionnaires and also the TADD aiming at assessing medium-term effects of the MI training in the alcohol craving and consumption levels.

Management and Ethics

Ethical requirements for human research will be followed in full accordance with the Code of Ethical Principles for Medical Research Involving Humans Subjects outlined in the Declaration of Helsinki (64th World Medical Association General Assembly, Brazil, 2013). The Ethics Committee for Social and Human Sciences of University of

Minho approved the present protocol in December 12, 2018 (approval reference: CE.CSH 078/2018). Prior to enrolling in the study, subjects will be informed about the aims, conditions and procedure of the study. Two copies of the informed consent forms will be provided, both of which will be signed by the researchers and participants. It is researchers' responsibility to guarantee the anonymity of the participants and the confidentiality of the data. The files containing data from the participants will be identified by the participant's code, not the name. The document containing the records of participants' personal information (e.g., names, contacts, code) will be stored in a different location from the data files and will only be accessible to authorized researchers. All files will be password protected and stored by the researchers in secure locations. Participants will be able to cease their participation in the study at any time without any consequences related to the relationship between the research team, the participant and the university. If participants want to terminate their enrollment in the study or ask for their data to be deleted later, researchers will promptly erase all data from files and eliminate documents using a paper shredder. There are no risks associated to the research protocol. College students will receive gift vouchers in order to compensate for their participation.

References

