**Discussion:** This protocol will provide the first behavioral and neurofunctional assessment of MI in BD. Along with poor MI abilities, BDs are expected to show alterations in the amplitude of several event-related potentials (ERPs) linked to MI (e.g., N2 and late parietal positivity) as well as abnormal functional connectivity (FC) patterns within/between regions associated with MI (e.g., DLPFC and hippocampal/parahippocampal regions). Results should also demonstrate the effectiveness of the training protocol, with BDs exhibiting an improved capacity to suppress alcohol-related memories after both *combined* and *cognitive* MI training, along with a significant reduction in alcohol use and craving in the short/medium-term. Furthermore, this protocol should also lead to significant modifications in the ERP and FC patterns, reflecting stronger MI capabilities and reduced alcohol cue reactivity in trained BD participants. Finally, in case the protocol provides significant results, these findings might have major implications for the understanding and treatment of alcohol misuse.

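### Three scales at 10 days are jointly called primary, with no choice among them, no adjustment and no between-arm test of follow-up scores, so the primary claim's false-positive rate exceeds 5%

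*Protocol*

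**What the plan says.** **What is primary.** Protocol section T5 states that ten days after the post-training EEG assessment "the primary craving and alcohol consumption outcomes will be assessed". It continues: "we will administer the PACS, the ACQ-SF-R and the AUDIT". The word primary is applied to outcomes nowhere else in the text read here.

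**What follows at 3 months.** The same section adds, as a further assessment, that "three months post-intervention, BDs will answer the same questionnaires and also the TADD". The stated purpose is to look at effects over the medium term, and this visit is not called primary.

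**The question and the claim.** Research question 4 (protocol, Quality assurance and randomization) covers both visits: "Will the MI training reduce alcohol consumption and craving levels at 10-day and 3-month follow-ups". The SAP Abstract expects better memory suppression after both kinds of training, "along with a significant reduction in alcohol use and craving in the short/medium-term". Neither says which scale, how many scales, or which visit must be positive.

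**Arms and size.** Protocol section T3 states that "BDs will be randomly assigned to one of the three training subgroups". The Target population section gives "45 non/low-drinkers and 45 BDs matched for age and gender". The allocation ratio is not stated.

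**Analysis.** The SAP's Statistical Analysis section compares T2 with T4 in the binge drinkers, and compares the three training groups at T4. AUDIT, PACS and ACQ-SF-R scores also enter correlations. No test of the 10-day or 3-month scores is described. The only multiplicity correction is a false discovery rate of 0.1 for the functional-connectivity links.

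**The concern.** Three outcomes share the primary label and no rule says how they combine into a conclusion. A report could rest the claim of reduced drinking or craving on whichever scale is significant, and that claim would not have a 5% error rate. Because no between-arm follow-up test is defined, the number of tests is also open: one three-arm test per scale, two comparisons with Control, or all three pairs. The 3-month visit offers four more scores on the same research question. The plan corrects for multiplicity in the connectivity analysis but not for the only outcomes it calls primary.

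**Working it through.** The documents state no significance level, power or familywise error rate for these outcomes, so there is no planned figure to reproduce.

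**Inputs from the documents**
- Scales called primary at 10 days: 3 (protocol, T5).
- Scales at 3 months: 3 + TADD = 4, not called primary (protocol, T5).
- Scale-visits if both are read for one claim: 3 + 4 = 7.
- Arms: 3. Randomised binge drinkers: 45.

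**Assumptions**
- Two-sided 0.05 per test.
- Equal allocation, 45 / 3 = 15 per arm.
- Normal scores with the same correlation r between any two scores.
- No true effect in either training arm.

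**Step 1: independent scores, one three-arm test each.** P(at least one false positive) = 1 − 0.95^k.
- k = 3: 1 − 0.95³ = 0.143.
- k = 7: 1 − 0.95⁷ = 0.302.

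**Step 2: correlated scores and pairwise testing.** In 40,000 simulated null trials per setting, the chance of at least one significant result was:

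| Scores and tests | r = 0 | 0.3 | 0.5 | 0.7 | 0.9 |
|---|---|---|---|---|---|
| 3 scales, three-arm test | 14.3% | 13.5% | 12.9% | 11.3% | 8.7% |
| 3 scales, each training arm vs Control (6 tests) | 25.0% | 23.8% | 21.9% | 19.5% | 15.1% |
| 7 scale-visits, three-arm test | 30.2% | 27.3% | 23.6% | 18.8% | 11.8% |
| 7 scale-visits, each training arm vs Control (14 tests) | 48.9% | 44.6% | 38.5% | 30.8% | 20.4% |

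**Step 3: favourable direction only.** At 0.025 per independent test, against a 2.5% standard:
- k = 3: 1 − 0.975³ = 7.3%.
- k = 7: 1 − 0.975⁷ = 16.2%.

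**Step 4: would adjusting only the three-arm tests be enough?** No. Suppose Combined training works strongly and Cognitive training does nothing. Every three-arm test then passes because of Combined. If arm-versus-Control results are next read at 0.05 each, the chance of a false Cognitive claim approaches, for independent scores, 1 − 0.95³ = 14% over three scales and 1 − 0.95⁷ = 30% over seven. Holm applied to the arm-versus-Control tests themselves holds this rate at about 5% or below.

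**The case against.** **The primary set is three scales, not seven.** A reader might infer that all seven scale-visits are primary. The documents do not support that. The label is tied to the 10-day visit; the 3-month visit is an addition with its own medium-term purpose, and TADD appears in follow-up only there. Research question 4 does join the visits, but it is last of four and not called primary. This objection stands, so the three-scale figures are the main result and the seven-score figures show what happens if the label is not respected.

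**A chance positive is not likely.** A reader might infer that a false primary result is more probable than not. In the table no figure reaches one half. Only testing all three pairs on all seven scale-visits at low correlation exceeds it (60% at r = 0, 55% at r = 0.3). Zero correlation is implausible in any case: PACS and ACQ-SF-R both measure craving, AUDIT and TADD both measure drinking, and three scales are repeated on the same people. This stands too.

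**The counted tests are not in the plan.** True: the test form, the 0.05 level and 15 per arm are assumptions. But an undefined set of tests leaves more room for selection, so this adds to the point.

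**The plan does compare arms on craving and consumption.** The SAP's third analysis step names these domains, so it would be wrong to say that no between-arm comparison of them is intended. It places that comparison at T4, however, not at the follow-up where the protocol puts the primary outcomes.

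**The direction matters.** The claim is a reduction, and a three-arm test has no direction. Counting favourable results only lowers the figures (Step 3), but they remain about three times the 2.5% standard for three tests.

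**Conclusion.** The point holds for the three 10-day scales. They are jointly primary, none is chosen, and the text read here gives neither an adjustment nor a between-arm test of the follow-up scores. At an assumed two-sided 0.05 and 15 per arm, the familywise error is about 11–14% with one three-arm test per scale and 19–25% with each training arm against Control (correlation 0.7 to 0). If the 3-month scores are read for the same claim, it is 19–30% and 31–49%. Higher correlation lowers every figure, but even at 0.9 the smallest in the table is 8.7%. The conclusion is that the rate exceeds 5% under every two-sided reading tested, not that a false positive is to be expected.

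**What to change.** Change the SAP wording as follows:

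1. Specify the between-arm comparison of the 10-day scores: the contrasts, the significance level and the sidedness.
2. Choose one of two routes:
   - Name one primary scale at 10 days. If both training arms are compared with Control on it, apply Holm over those two comparisons.
   - Keep all three scales and apply Holm across the six arm-versus-Control comparisons (3 scales × 2 training arms). Adjusting only the three-arm tests is not enough, as Step 4 shows.
3. Label the 3-month scales, including TADD, as secondary.

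No new data, visits or participants are needed. The cost is a stricter threshold. Under Holm over six, the smallest p-value must be at most 0.05 / 6 = 0.0083; with one scale and two comparisons it must be at most 0.05 / 2 = 0.025. With 45 randomised participants that loss of power matters, which favours naming one scale.

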consumed per hour], number and type of drinks consumed in a standard week, percentage of times getting drunk when going out, age of onset of regular and BD) to assess participants' drinking patterns; 2) the DUDIT-E to examine the consumption of other drugs; 3) the Penn Alcohol Craving Scale (PACS) and the Alcohol Craving Questionnaire-Short Form Revised (ACQ-SF-R) to assess the alcohol craving; 4) the Barratt Impulsivity Scale-11 (BIS-11) and the short form of the Urgency-Premeditation-Perseverance-Sensation Seeking-Positive Urgency (UPPS-P) impulsive behavior scale to assess participants' impulsiveness; 5) the Symptom Checklist-90-Revised questionnaire (SCL-90-R) to evaluate the presence of psychopathological traits; 6) a clinical history interview to explore the personal/family history of psychopathological and neurological disorders as well as the overall medical history of the participants; and 7) the Edinburgh Handedness Inventory (EHI) to evaluate the participants' handedness.

T2: Pre-training EEG Assessment

During the pre-training EEG assessment, psychological (i.e., craving levels), behavioral (i.e., alcohol consumption levels and task performance) and neurofunctional (e.g., ERPs, brain FC) outcomes will be assessed. EEG data will be collected while participants perform the ACR and the TNTA task. Before the EEG recording, participants will be asked to perform a breathalyzer test to ensure that blood alcohol concentration value is 0.0% (Alcoscan ALC-1). Along with the AUDIT, and in order to determine alcohol consumption levels during the previous week and the previous three months, we will administer the Alcohol Timeline Followback (TLFB) and the Typical and Atypical Drinking Diary (TADD), respectively. After filling in the questionnaires, participants will perform the ACR task. Participants' resting brain activity will be recorded for three minutes during eyes-closed prior to the TNTA task. Finally, they will perform the TNTA

task. The total duration of the pre-training EEG assessment will be approximately two and a half hours.

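### At the 10-day follow-up the AUDIT is the only consumption instrument; the past-week measure (TLFB) taken at T2 is not repeated, so no measure with a stated short recall window covers the days after training.

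*Protocol*

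**What the plan says.** Research question 4 (Protocol, Quality assurance and randomization) reads: "Will the MI training reduce alcohol consumption and craving levels at 10-day and 3-month follow-ups".

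At baseline (Protocol, T2: Pre-training EEG Assessment) consumption is measured with three tools. The AUDIT is given, and the TLFB and TADD are added "in order to determine alcohol consumption levels during the previous week and the previous three months", in that order.

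At follow-up (Protocol, T5) the text is "Ten days after the post-training EEG assessment, the primary craving and alcohol consumption outcomes will be assessed", and to do this "we will administer the PACS, the ACQ-SF-R and the AUDIT". At three months "BDs will answer the same questionnaires and also the TADD".

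For the post-training EEG visit (Protocol, T4), "participants will perform the ACR and TNTA tasks under the same procedure to the one undertaken during the T2"; no questionnaire is named. The SAP Abstract places the measurement of alcohol use at the first EEG assessment, 10 days and 3 months. The SAP Statistical Analysis section names the AUDIT, and no other tool, as the consumption measure.

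**The concern.** The protocol's baseline battery shows that its authors wanted consumption over two defined windows in addition to the AUDIT. One of those windows, three months, is carried forward to the 3-month visit. The other, one week, suits a visit 10 days after T4 but is not carried forward. The T2 TLFB is thus a baseline with no counterpart at either follow-up visit.

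At stake is the short-term half of research question 4. If the AUDIT looks back further than 10 days, its 10-day score mixes drinking before and after T4, and a real early change would appear smaller than it is. With 45 binge drinkers in three groups (about 15 each if split equally), there is little room for such dilution. Consumption in that week cannot be reconstructed reliably afterwards.

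**Working it through.** The plan states no figure to reproduce on this point. The check is the schedule of consumption instruments, followed by a short illustration.

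**Step 1: instrument by visit** (Protocol, sections T1, T2, T4 and T5)

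| Instrument | Stated window | T1 | T2 | T4 | 10 days | 3 months |
|---|---|---|---|---|---|---|
| AUDIT | none given | yes | yes | not named | yes | yes |
| TLFB | previous week | no | yes | not named | no | no |
| TADD | previous three months | no | yes | not named | no | yes |

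The 3-month visit has a tool with a stated window and a matching T2 baseline (TADD). The 10-day visit has a tool with a T2 baseline (AUDIT) but none with a stated window.

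**Step 2: how much of a look-back falls after T4**

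For a look-back of W days at a visit 10 days after T4, the share after T4 is min(1, 10/W). Because the documents give no AUDIT recall period, W is an assumption and is shown as a range. The last column further assumes a score proportional to drinking over the look-back and a true 20% reduction that starts at T4, so the apparent reduction is 20% × share.

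| Assumed W (days) | Share after T4 | Apparent reduction |
|---|---|---|
| 7 | 100% | 20% |
| 30 | 10/30 = 33% | 6.7% |
| 90 | 10/90 = 11% | 2.2% |
| 365 | 10/365 = 2.7% | 0.5% |

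Dilution begins once W exceeds 10 days. An effect that began during training, before T4, would be diluted somewhat less.

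**Step 3: the TLFB at 10 days**

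With W = 7, the whole window lies after T4 and has a like-for-like T2 baseline. It covers 7 of the 10 days.

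**Step 4: what the 10 days are counted from**

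Section T5 counts from the post-training EEG assessment; the SAP Abstract counts from training. A 7-day look-back at day 10 lies wholly after training on either count. If the count is from training, whether it also lies wholly after T4 depends on the gap between training and T4, which the documents do not give.

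**The case against.** **The AUDIT already measures consumption at 10 days.** This stands, and it limits the point. A reader might infer that short-term consumption goes unmeasured after training. The documents do not support that: section T5 gives the AUDIT for exactly this purpose, the SAP treats it as the consumption measure, and it has a T2 baseline. What is missing is a measure with a stated short window.

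**The harm is unproven.** This stands in part. The range in Step 2 runs from no dilution to near-complete dilution, and nothing in the documents places the AUDIT within it. A reader might take the 11% as a property of the 10-day visit, on the ground that the TADD covers three months. The TADD is not scheduled at 10 days, so the figure says only what would follow if the AUDIT recall were 90 days.

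**The TLFB may be repeated at T4.** The same-procedure wording could be stretched to include the T2 questionnaires, and the SAP Statistical Analysis section plans a comparison of the groups at T4 that extends to craving and consumption. Against this, the protocol sentence concerns the two tasks, and the SAP Abstract does not list T4 for alcohol use. The documents disagree here. The 10-day gap remains on either reading, because a past-week TLFB at T4 looks back from T4 and not over the days after it.

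**One week is a noisy measure.** This stands. Eligibility requires only one binge occasion a month. At that threshold, assuming a constant rate and a 30-day month, the chance of any binge in a given week is 1 − exp(−7/30) = 21%. With about 15 per group, the weekly measure would be sparse and its T2 value a weak covariate. This argues against putting the TLFB in place of the AUDIT, but not against adding it.

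**Conclusion.** The point holds in a limited form. The past-week tool is named only at T2. The AUDIT is the only consumption instrument at the 10-day visit, and no measure with a stated short recall window is given there, although research question 4 asks about that time point and section T5 calls its outcomes primary.

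The size cannot be fixed from the documents. It is nil if the AUDIT recall is 10 days or less and grows with longer recall, to 2.7% of the look-back falling after T4 at an assumed 365 days. The illustrated loss of effect also assumes proportional scoring and a change that starts at T4.

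A reader might go on to conclude that the TLFB should become the 10-day outcome in the AUDIT's place, or that it is also needed at 3 months. Neither follows. The first trades one limitation for another in participants who may binge only about monthly; the second adds little where the TADD already matches T2. This is an inexpensive improvement to the schedule and not a defect that invalidates the trial. Parts of the SAP ahead of its Abstract were not available for this check.

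**What to change.** 1. In Protocol section T5, add the T2 form of the past-week TLFB at the 10-day contact, as an additional consumption outcome alongside the AUDIT.
2. In the SAP, state that 10-day TLFB consumption will be compared between the three training groups with T2 TLFB as covariate. The Statistical Analysis section sets out comparisons at T2 and T4 but no explicit model for the 10-day data, so this needs its own line.
3. State the recall period of the AUDIT as administered, so that readers can see which days its 10-day score covers.
4. Reconcile whether the 10 days run from T4 (Protocol, T5) or from training (SAP, Abstract), and whether consumption is measured at T4 (SAP, Statistical Analysis against Abstract).

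The cost is a short amendment and a few minutes of participant time, with a questionnaire already in use and a contact already planned. The limits to accept are a noisy one-week measure and coverage of 7 of the 10 days.
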